### **13.1.4 Deaths**

Details of any deaths will be listed together with SAEs as detailed in 13.1.1.

### **13.2 Drug exposure**

Exposure to emapalumab, anakinra and methylprednisolone background therapy, respectively, will be summarized with descriptive statistics.

### **13.3 Laboratory data**

The laboratory data evaluation will be based on the results from the local laboratories. For potential queries of laboratory data outside of reference ranges,  $\pm 10$  percent will be allowed to account for variability of certain lab parameters in the different local laboratories.

The laboratory safety data will be presented as actual values and change from baseline values over time by descriptive statistics. The number and percentage of patients with low, normal, or high laboratory values at baseline versus subsequent visits will be presented using shift tables.

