5.2 Discussion of study design, including the choice of control groups

5.3 Selection of study population

5.3.1 Inclusion criteria

A patient must fulfill the following criteria in order to be included in the study:

- 1. Signed informed consent provided by the patient, or by the patient's legally authorized representative(s), as applicable.
- 2. Documented presence of SARS-CoV-2 infection as per hospital routine.
- 3. Age > 18 to < 85 years at the time of screening.
- 4. Presence of respiratory distress, defined as:
 - a. $PaO_2/FiO_2 < 300 \text{ mm Hg and } >200 \text{ mm Hg or}$
 - b. RR \geq 30 breaths/min or
 - c. $SpO_2 < 93\%$ in air at rest.

Note: Patients given CPAP ventilator support are eligible for inclusion.

- 5. Presence of hyperinflammation defined as:
 - a. Lymphocyte counts:
 - < 1000 cells/ μ L, in patients who have not received systemic glucocorticoids for at least 2 days prior to the assessment of the lymphocyte count
 - < 1200 cells/ μ L, in patients who have received systemic glucocorticoids for at least 2 days prior to the assessment of the lymphocyte count

and

- b. One of the following three criteria:
 - i. Ferritin > 500ng/mL
 - ii. LDH > 300 U/L
 - iii. D-Dimers > 1000 ng/mL

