5.5.4.3 Reporting requirement of adverse events

5.5.4.3.1 Reporting of adverse events

Irrespective of seriousness, the following adverse events are considered as adverse events of special interest and must be reported on AE page of the CRF.

In all patients:

• AEs leading to discontinuation of study treatment

Infusion related reactions including anaphylactic/anaphylactoid reactions. In patients treated with emapalumab, the following AEs will be considered of special interest:

• All new infections.

In patients treated with anakinra, the following AEs will be considered of special interest:

• Severe neutropenia defined as neutrophil count $< 0.5 \times 10^{9}$ /l.

No other AEs are required to be reported on the AE page of the CRF

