5.5.4.7 Electrocardiograms

A 12-lead ECG recording will be performed at screening, Visit 6 (Day 15) and Visit 7 (Day 28), and recorded in the CRF. The ECG assessments will be performed at site and will be reported as "normal" or "abnormal". Any abnormalities should be specified. Abnormalities reported at screening should be recorded as medical history.

For AE reporting of abnormalities, see Section 5.5.4.3.

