### 3.4.3 Safety endpoints

Safety endpoints of this study are:

- Treatment-emergent serious adverse events (SAEs).
- Adverse events leading to premature discontinuation of study treatment.
- Infusion related reactions including anaphylactic/anaphylactoid reactions.
- Treatment emergent adverse events of special interest:
  - Emapalumab treatment group: All new infections.
  - Anakinra treatment group: Severe neutropenia.
- Treatment-emergent laboratory abnormalities.
- Presence of anti-drug antibodies (ADAs) against emapalumab and anakinra, and presence of neutralizing antibodies (Nabs) against anakinra.

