### **13.5 ECG**

ECG will be presented as absolute and change from baseline values by visit with descriptive statistics.

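### SAP 13.5 plans numeric ECG summaries from normal/abnormal data, and SAP 13.3 gives no patient-level, three-arm count of newly severe laboratory values

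*SAP*

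**What the plan says.** **Laboratory.** SAP 3.4.3 lists "Treatment-emergent laboratory abnormalities" as a safety endpoint, as does Protocol 4.2.1. Neither document defines the term. SAP 13.3 plans two displays. The first reads "The laboratory safety data will be presented as actual values and change from baseline values over time by descriptive statistics". The second reads "The number and percentage of patients with low, normal, or high laboratory values at baseline versus subsequent visits will be presented using shift tables". SAP section 8 sets descriptive statistics for continuous data as n, mean, SD, median, minimum and maximum. SAP 12.2.7 and 12.2.8 add ANCOVA of change at Day 15 for the same laboratory parameters, treated there as efficacy variables.

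**ECG.** SAP 13.5 states: "ECG will be presented as absolute and change from baseline values by visit with descriptive statistics". Protocol 5.5.4.7 states: "The ECG assessments will be performed at site and will be reported as" normal or abnormal, with any abnormality specified. Recordings are at screening, Day 15 and Day 28.

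**Adverse-event reporting.** Protocol 5.5.4.3.1 limits the AE page to a short list of special-interest events. One entry begins "In patients treated with anakinra, the following AEs will be considered of special interest" and names severe neutropenia, below 0.5 × 10^9/L. Protocol 5.5.4.3.2 adds SAEs, but does not require the listed laboratory variables to be reported as SAEs.

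**The concern.** The ECG table asks for quantities that the protocol does not collect. The laboratory tables serve a patient-level endpoint (who developed an abnormality on treatment) with displays that either describe the group or use three classes without severity.

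The entry criteria make abnormal starting values likely for some analytes, and those are the patients for whom a low/normal/high table says least. Because most laboratory events are kept out of AE and SAE reporting, the laboratory tables are the main place where a liver or cytopenia signal could be compared between arms. At stake is whether a reader of the report can see how many patients per arm became newly severe. The efficacy conclusion is not affected.

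**Working it through.** The plan states no figure on this point, so the check compares the data collected with the tables planned. It then passes example values through the planned classification.

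**1. ECG.**

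| Item | Source | Content |
|---|---|---|
| Collected | Protocol 5.5.4.7 | normal/abnormal, abnormality specified; no rate or interval named |
| Planned | SAP 13.5 | absolute and change-from-baseline values by visit |
| SAP rule for categorical data | SAP section 8 | counts and percentages |
| Similar item | Protocol 5.5.3.6, SAP 12.2.6 | chest imaging, recorded normal/abnormal, given a shift table |

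A two-level result has no mean, SD or numeric difference. A shift from screening to each later recording can be produced.

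**2. What the three-class shift separates.** A value is low if below the lower limit (LLN), high if above the upper limit (ULN), and otherwise normal. The documents give no reference ranges. ALT is therefore expressed in multiples of ULN, and the neutrophil LLN is assumed to lie between 1.5 and 2.0 × 10^9/L; both ends give the same classes.

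| Analyte | Baseline → later | Change | Shift cell |
|---|---|---|---|
| ALT (× ULN) | 4.9 → 20 | +15.1 | high → high |
| ALT | 4.9 → 1.2 | −3.7 | high → high |
| ALT | 0.9 → 1.2 | +0.3 | normal → high |
| Neutrophils (× 10^9/L) | 4.0 → 1.4 | −2.6 | normal → low |
| Neutrophils | 4.0 → 0.4 | −3.6 | normal → low |
| Neutrophils | 1.4 → 0.4 | −1.0 | low → low |

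Large worsening and clear improvement can share a cell, and a trivial change can count as a shift. Among patients who start normal, mild and severe falls are not distinguished.

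**3. Who may start abnormal.** Protocol 5.3.2 excludes AST or ALT only above 5 × ULN, so values between 1 and 5 × ULN may enter. Protocol 5.3.1 requires lymphocytes below 1000 cells/µL "in patients who have not received systemic glucocorticoids for at least 2 days prior to the assessment of the lymphocyte count", or below 1200 "in patients who have received systemic glucocorticoids for at least 2 days prior to the assessment of the lymphocyte count". With an assumed LLN of 1000 to 1500, a count of 999 is low throughout. A count of 1199 is normal if the LLN is 1000, and low if it is 1200 or 1500. At least one of ferritin, LDH and D-dimers must also exceed its entry threshold.

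**4. What the other laboratory displays add.** By-visit minimum and maximum show the most extreme selected value, but not how many patients were severe or whether this was new. In a planned arm of 18, a maximum of 20 × ULN is compatible with one patient above 5 × ULN (1/18 = 5.6%) or five (5/18 = 27.8%). SAP 8.1 takes the value closest to the scheduled day and averages same-day numeric values, so an unscheduled peak or nadir may not be the one shown. SAP 8.1 also has a rule that uses all post-baseline values for extreme-value summaries, but SAP 13.3 plans no such summary.

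**5. Other routes to a count.** The list exempted in Protocol 5.5.4.3.2 covers the routine blood tests in Protocol Table 3. Discontinuation of study treatment triggers an AE report, but the standard-of-care arm has no study drug to discontinue. Severe neutropenia is of special interest under anakinra only (Protocol 5.5.4.3.1, SAP 13.1.3), so that count has no counterpart from the same source in the other arms. SAP 12.2.7 counts patients whose ferritin, LDH or D-dimers improve or normalize; no section counts patients who worsen past a limit.

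**The case against.** The strongest reply is that the laboratory data are well displayed. By-visit statistics include minimum and maximum for both values and changes, SAP 12.2.8 adds quartiles and ANCOVA, and SAP 8.1 provides listings of all values contributing to a time point. Arms of 18 can be read line by line. Differential counts are taken in every arm, and severe neutropenia under anakinra has its own table. This stands, and it rules out several stronger readings:

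- A reader might infer that worsening is invisible or that the SAP cannot show a liver or cytopenia signal. The group-level extremes and listings contradict that.
- A reader might infer that every patient starts low for lymphocytes, so that no worsening can register. This depends on local lower limits that the documents do not give. Also, eligibility results may be up to 72 hours old, while a new sample is drawn at Visit 1, so the baseline value need not be the eligibility value.
- A reader might infer that low neutrophils are usual at entry. No entry criterion implies this.
- A reader might infer that no ECG table is possible. Counts and percentages are; only the numeric values and their change are not.

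It can also be said that 5 × ULN is an enrolment limit, so a single cut there would count 4.9 → 5.1 and miss 0.9 → 4.8. That is a fair argument for graded categories rather than one threshold. None of these replies supplies a definition of the endpoint or a count by patient and arm.

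**Conclusion.** The point holds in two limited parts.

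1. **ECG.** Protocol 5.5.4.7 and SAP 13.5 conflict and must be reconciled. As described, no patient has a numeric ECG value to summarise. This assumes that the CRF follows the protocol and records no intervals.
2. **Laboratory.** A named safety endpoint has no definition, and no planned table gives the number of patients per arm whose worst value is newly severe. The three-class shift cannot fill this gap for an analyte already abnormal in the same direction, and it does not grade severity for the rest. The restriction applies per analyte and direction. How many patients it touches cannot be calculated, because baseline distributions and local ranges are not given.

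This is worth correcting before the safety tables are produced. It does not bear on the primary endpoint, type I error or power.

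**What to change.** **SAP 13.5.** Replace the numeric summary with a normal/abnormal shift table from screening to Day 15 and to Day 28, by arm, with a listing of the specified abnormalities.

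**SAP 13.3.** Define a treatment-emergent laboratory abnormality as a worst post-baseline value, scheduled or unscheduled under the extreme-value rule in SAP 8.1, in a more severe category than at baseline. Tabulate number and percentage for all three arms.

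- Use graded or multiple-of-ULN/LLN categories for neutrophils, lymphocytes, platelets, Hb, AST/ALT, bilirubin and creatinine.
- Include among the cut-points the limits already in the protocol: neutrophils below 1.0 and below 0.5 × 10^9/L, and AST or ALT above 5 × ULN. They serve tabulation only and change no clinical rule.
- If a renal-function category is added, name the formula. Protocol 5.3.2 uses estimated glomerular filtration rate, and Protocol 5.5.4.13 uses creatinine clearance.
- Show how many patients have a post-baseline value, and repeat the table on scheduled samples only. In an open-label trial the arms may differ in unscheduled testing.

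The existing by-visit statistics and shift tables can stay. The cost is SAP wording and one or two extra tables. No new data are needed, because the low/normal/high classes already require the local limits.

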### **13.4 Vital signs**

Vital signs will be presented as absolute and change from baseline values by visit with descriptive statistics.

### **13.5 ECG**

ECG will be presented as absolute and change from baseline values by visit with descriptive statistics.

